6.3 SAFETY ANALYSIS SET

The safety analysis set includes all randomized subjects who received at least 1 dose of IP.

All safety analyses will be conducted on this analysis set according to actual treatment received.

7. INTERIM ANALYSES

A safety analysis will be performed by the DMC after the first 12 subjects have received at least 2 doses of IP.

No interim analyses of efficacy or pharmacodynamics are planned.

8. DATA REVIEW

8.1 DATA HANDLING AND TRANSFER

Data will be entered electronically into a database built with Medidata Rave and exported as SAS[®] version 9.1.3 or higher datasets. Converted datasets will be created using SAS[®] and following standard Clinical Data Interchange Standards Consortium Standard Data Tabulation Model (CDISC SDTM, version 1.3, Implementation Guide version v3.1.3) conventions. Analysis datasets will be created using SAS[®] and following CDISC Analysis Data Model (ADaM, version 2.1, Implementation Guide 1.0) standards.

Medical history and AEs will be coded using the current version of Medical Dictionary for Regulatory Activities (MedDRA) to assign a system organ class (SOC) and preferred term (PT) to each event. Adverse events and abnormal laboratory results considered as AEs are assigned a toxicity grade according to National Cancer Institute (NCI-US) - Common Terminology Criteria for Adverse Events (CTCAE) version 4.03. Prior and concomitant medications will be coded using the current version of World Health Organization Drug Dictionary (WHO-DD).

Additional details can be found in the PRA Clinical Informatics Plan for this study.

8.2 DATA SCREENING

Beyond the data screening built into the PRA Clinical Informatics Plan, the PRA programming of analysis datasets and Tables, Figures, and Listings (TFLs) provides additional data screening. Presumed data issues will be output into SAS[®] logs identified by the word “Problem” and extracted from the logs by a SAS[®] macro and sent to the Data Management team for review.

Review of a post-freeze dry run of TFLs on clean subjects will allow for further data screening prior to database lock. The dry run will be discussed with the sponsor in a data review meeting to identify any final data issues and seek corrections prior to database lock. The PRA statistician and the sponsor must approve database lock.

9. STATISTICAL METHODS

All statistical analyses will be performed using SAS[®] Version 9.1.3 or higher.

Unless otherwise specified, descriptive data summaries will be tabulated by treatment for all endpoints. For continuous outcomes, the descriptive statistics include number of subjects with observations (n), mean, standard deviation, median, 25th percentile (Q1), 75th percentile (Q3), minimum, and maximum. The mean, median, Q1, and Q3, will be presented to one decimal place greater than the original data, standard deviation will be to two decimal places greater than the original data, and the minimum and maximum will have the same number of decimal places as the original data.

Categorical outcomes will be summarized by number and percent of subjects falling into each category. Percentages will be rounded to one decimal place except for 100%, which will have no

decimal place. Kaplan-Meier (KM) estimates of quartiles will be provided for time-to-event endpoints.

9.1 SUBJECT DISPOSITION

The following information will be summarized for subject disposition and accountability for each of the analysis sets defined in [Section 6](#), unless stated otherwise:

- Number of subjects randomized will be tabulated by region, country, and site (for the FAS)
- Subject disposition (including number of subjects who were treated with ABP 798/rituximab, completed all planned IP doses, discontinued IP early with reason for discontinuation, completed study, and discontinued study early with reason for discontinuation)
- Summary of analysis populations with reason for exclusion (for all screened subjects)
- Number and percent of subjects on study at each visit
- Randomization list of subjects and their actual versus randomized treatment group (for the FAS)

9.2 PROTOCOL DEVIATIONS AND VIOLATIONS

Protocol deviations and violations (PDV) data will be entered into the Clinical Trials Management System (CTMS). The study team will conduct on-going reviews of the PDV data from CTMS and the resulting set of subjects to be included in the PP analysis set throughout the study, adjusting the PDV criteria as seems appropriate. The subjects to be included in the PP analysis set must be finalized at the post-freeze data review meeting (or earlier), prior to database lock.

Based on the PDV data entered into CTMS, the major protocol deviations, thought to potentially impact the statistical analyses or subject safety, will be listed and tabulated using incidence and percentages by deviation type, deviation, and randomized treatment group. A summary of inclusion/exclusion criteria deviations will also be provided. See the protocol deviation guidance document for details on specific deviation types and deviations.

9.3 TREATMENTS

All analyses in this section will be performed on the safety analysis set based on a subject's actual treatment received.

9.3.1 Extent of Study Drug Exposure

Summary statistics will be provided for the total number of IP doses administered and the total duration of IP exposure throughout the study. The overall incidence of IP dose delays, dose

interruptions, and withheld doses as well as the reasons will be tabulated. The numbers of subjects receiving a full or partial dose and subjects with a dose interruption for each dosing instance will also be provided.

A listing of the lot number(s) for IP for each subject and a listing of unique manufacturing lot numbers will be provided.

9.3.2 Concomitant Medications

Concomitant medications include all medications and therapies during the study except for planned IP administration. Concomitant medications will be coded by WHO-DD and will be summarized by preferred name and actual treatment group from study day 1 through the end of study. Medications with a stop date before study day 1 will not be summarized.

9.3.3 Medical History

Medical conditions at screening will be summarized by PT and primary SOC separately by status (unresolved versus resolved).

9.4 DEMOGRAPHIC AND BASELINE CHARACTERISTICS

Subject demographics, baseline characteristics, and randomization stratification factors will be summarized descriptively by treatment group in each of the analysis sets defined in [Section 6](#).

The following demographics and baseline characteristics and stratification factors will be summarized:

- age (in years, at time of signing informed consent), and age group (≤ 60 vs. >60)
- race (American Indian or Alaska native vs. Asian – Non-Japanese vs. Asian – Japanese vs. Black or African American vs. Native Hawaiian or other Pacific Islander vs. White vs. Other)
- gender (male vs. female)
- ethnicity (Hispanic vs. non-Hispanic vs. Not allowed to collect)
- geographic region (Eastern Europe vs. Western Europe/Other vs. North America vs. Japan)
- height
- weight
- Eastern Cooperative Oncology Group (ECOG) performance status (0 vs. 1 vs. 2 vs. 3 vs. 4)
- time since original diagnosis in months

- staging of original diagnosis (Stage I vs. II vs. III vs. IV vs. IE vs. IIE vs. IIIE vs. IIIES vs. IIIS vs. Unknown)
- staging at screening (Stage II vs. III vs. IV vs. IIE vs. IIIE vs. IIIES vs. IIIS)
- staging subclassification (A vs. B)
- histologic grade at screening (I vs. II)
- previous radiation treatment (yes vs. no)
- time since last dose of prior radiation in months
- presence of B symptoms (yes vs. no)
- bone marrow involvement (yes/indeterminate vs. no)
- LDH (<lower limit of normal vs. >upper limit of normal vs. within normal range)
- # of nodal sites
- # of extranodal sites
- FLIPI score (0 vs.1 vs. 2 vs. 3 vs. 4 vs. 5)
- FLIPI (low vs. intermediate vs. high)

9.5 EFFICACY ANALYSES

9.5.1 Primary Variable

9.5.1.1 PRIMARY ANALYSIS

The primary analysis of ORR by week 28 will be based on the FAS according to randomized treatment, using data from the central, independent, blinded radiologists' and oncologist's assessments.

Clinical equivalence of the primary endpoint will first be demonstrated by comparing the 1-sided 95% lower confidence limit of the RD of ORR by week 28 between ABP 798 and rituximab with a noninferiority margin of -15%. If this is successful, the 1-sided upper 95% confidence limit of the RD of ORR by week 28 will be compared with a nonsuperiority margin of +35.5%.

To estimate the 1-sided 95% confidence limits of the RD of ORR by week 28, the generalized linear model adjusted for the stratification factors (geographic region and age group) will be fitted using the SAS[®] procedure "GENMOD". A sample SAS code fragment is provided below for reference:

```
proc genmod data=<data> descending;  
  class trt <categorical_var>;  
  model <binary var> = trt <categorical_var> stratification factors
```

```
<categorical_var>/ dist=binomial link=identity;  
estimate 'label of the estimate' trt -1 1 / alpha=0.1 ;  
run;
```

In addition, a 2-sided 95% confidence interval (CI) will be calculated and evaluated against a symmetrical margin of 15% for noninferiority and nonsuperiority.

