9.5.1.2 SECONDARY ANALYSIS

To assess the robustness of the primary ORR analysis results, the primary analysis will be repeated using the central, independent, blinded radiologists' and oncologist's assessments on the PP analysis set according to actual treatment received and using the FAS and the investigator's assessment of disease.

The RD for ORR by week 28 will also be examined in the subgroups as defined by the baseline covariates in [Section 4.4](#). A forest plot will be created to summarize the variability in the RDs across the subgroups. In each case, the RDs and both 90% and 95% CIs will be calculated using the methods described in [Section 9.5.1.1](#).

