9.5.5 Secondary Variables

9.5.5.1 RISK DIFFERENCE FOR OVERALL RESPONSE RATE AT WEEK 12

The RD for ORR at week 12 will be summarized the same way as the analyses described in [Section 9.5.1](#). Subjects without a disease assessment at week 12 will be counted as nonresponders in calculating the RD for ORR at week 12.

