9.6 PHARMACOKINETICS

Serum ABP 798 and rituximab concentrations will be summarized descriptively by treatment for each sampling visit using the safety analysis set.

The 90% CI for the geometric mean ratio (GMR) of test (ABP 798)-to-reference (rituximab) for serum concentrations at predose (trough) and immediately after the end of infusion at week 12 will be calculated.

The point estimates and 90% CI for the GMR for each visit will be estimated using an analysis of covariance model adjusted for the stratification factors as covariates as defined in [Section 4.4](#). Sample SAS code for PROC MIXED is displayed below:

```
PROC MIXED;  
  CLASS treatment <stratification variables>;  
  MODEL Natural Log PK concentration = treatment <stratification variables>;  
  ESTIMATE 'ABP 798 vs rituximab' Treatment 1 -1 / e ci alpha=0.1;  
RUN;
```

The geometric least squares mean for each treatment will be presented. The ratios of the geometric means for the comparison of the test treatment to the reference treatment will be obtained by exponentiating the difference of the means on the natural log scale. Ninety percent CIs will be obtained by exponentiating the CI for the difference between the means on the log scale.

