9.8.6 Progression-free Survival

The primary analysis of PFS will be based on disease assessments determined by the central, independent, blinded radiologists' and oncologist's review.

The LIFETEST procedure in SAS[®] will be used to produce estimates of quartiles and 95% CIs via the method of [Brookmeyer and Crowley \(1982\)](#) and to produce KM survival plots. The standard error of the KM quartile estimates will be estimated using Greenwood's formula ([Kalbfleisch and Prentice, 1980](#)).

Estimates of the hazard ratio (HR) for treatment and the corresponding 1-sided 95% and 97.5% CIs will also be presented. They will be estimated using the stratified Cox proportional hazards regression model using the PHREG procedure in SAS[®]. The model will be stratified by the randomization stratification factors. HRs will be calculated using the rituximab arm as the reference group.

Progression-free survival will also be summarized based on the investigator assessment of progression.

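### Could the opposite contrast signs in the SAP's sample code turn the primary risk difference the wrong way round?

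*SAP*

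**What the plan says.** SAP section 9.5.1.1 compares the one-sided 95% lower confidence limit of the "RD of ORR by week 28 between ABP 798 and rituximab with a noninferiority margin of -15" per cent. If that succeeds, the one-sided 95% upper limit is compared with a nonsuperiority margin of +35.5%. Protocol section 12.6.4 states the same rule. A two-sided 95% interval is also set against a symmetric 15% margin.

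The limits come from a binomial identity-link model. The illustrative code declares "class trt <categorical_var>" and then "estimate 'label of the estimate' trt -1 1 / alpha=0.1". The text of the label is a placeholder, and no level order is given.

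Section 9.6 has a second illustration, for the pharmacokinetic model: "ESTIMATE 'ABP 798 vs rituximab' Treatment 1 -1 / e ci alpha=0.1". It has no level order either, but its label names the comparison, and the prose defines the "geometric mean ratio (GMR) of test (ABP 798)-to-reference (rituximab"). For the hazard ratios, section 9.8.6 states: "HRs will be calculated using the rituximab arm as the reference group".

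The RD method carries over to other analyses. For subgroups, "the RDs and both 90% and 95% CIs will be calculated using the methods described in" section 9.5.1.1, and "The RD for ORR at week 12 will be summarized the same way as the analyses described in" section 9.5.1.

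**The concern.** The coefficients -1, 1 take the second treatment level minus the first. The coefficients 1, -1 take the first minus the second. If both models used one treatment coding, exactly one of the two lines would run opposite to the intended direction. The SAP does not say which, because no coding is shown.

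Of the three effect measures, the RD is the only one without a written direction, and it is the one that decides the trial. With symmetric margins a sign flip would not alter the verdict. With -15% and +35.5% it exchanges the tolerated deficit for the tolerated excess: on the ABP 798 minus rituximab scale the margins become -35.5% and +15%. The same convention feeds the per-protocol, investigator-assessed, subgroup and week 12 RDs.

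**Working it through.** **Inputs.** There are 125 subjects per arm (SAP section 3). The margins are -15% and +35.5%, and alpha = 0.1 two-sided gives 0.05 per side, z = 1.645 (SAP section 9.5.1.1), which matches the stated one-sided 95% limits. The response rate and power behind the sample size are not in the public text, so the response rates below are assumptions.

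**Step 1: which direction does the rule allow?** Response is a benefit.

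| RD read as | Lower limit above -15% shows | Upper limit below +35.5% shows |
|---|---|---|
| ABP 798 minus rituximab | ABP 798 is less than 15 points worse: noninferiority | ABP 798 is less than 35.5 points better: nonsuperiority |
| rituximab minus ABP 798 | ABP 798 is less than 15 points better: nonsuperiority | ABP 798 is less than 35.5 points worse: noninferiority |

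The plan calls the first test noninferiority and the second nonsuperiority. Only the first row fits, so the prose fixes the direction without an explicit subtraction.

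**Step 2: what do the two code lines imply?** If the levels are ordered ABP 798 then rituximab, the RD line returns rituximab minus ABP 798 and the PK line is right. If they are ordered rituximab then ABP 798 (for instance 0 and 1), the RD line is right and the PK line returns the reciprocal ratio. The variables have different names (trt and treatment) and hold different things: randomized assignment in the full analysis set for response, and actual treatment in the safety set for PK (Protocol section 12.6.5). If they are coded in opposite order, both lines are right.

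**Step 3: the size of a reversal, if one occurred.** With unpooled standard error se and true RD d (ABP 798 minus rituximab),

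P(pass) = Phi((hi - d)/se - 1.645) - Phi((lo - d)/se + 1.645).

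Take a rituximab rate of 80% and d = -15%. Then se = sqrt(0.80 x 0.20/125 + 0.65 x 0.35/125) = 0.0557.
- Intended (-15%, +35.5%): Phi(7.42) - Phi(1.645) = 5.0%.
- Reversed (-35.5%, +15%): Phi(3.74) - Phi(-2.04) = 97.9%.

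Exact enumeration of all 126 x 126 outcomes, with unadjusted Wald limits and rituximab rates of 75/80/85%, agrees:

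| True RD | Passes, intended sign | Passes, reversed sign |
|---|---|---|
| 0 | 86.5/90.7/95.2% | the same |
| -15 points | 4.9/5.1/5.1% | 97.1/98.1/98.9% |
| -25 points | 0.05/0.03/0.03% | 56.0/57.6/61.8% |

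For identical products the pass rate does not depend on direction, but the verdict in an individual trial would, in 27/19/10% of trials.

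**Step 4: would a reversal be visible?** Take 75/125 (60%) on ABP 798 and 100/125 (80%) on rituximab. Then se = sqrt(0.60 x 0.40/125 + 0.80 x 0.20/125) = 0.0566. The RD is -20.0%, with 90% limits -20.0 -/+ 1.645 x 5.66 = -29.3% to -10.7%, which fails. Reversed, it is +20.0% (10.7% to 29.3%) and would pass, but that positive RD would stand next to arm rates of 60% and 80%.

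The symmetric check does not depend on sign. Here the 95% interval is -20.0 -/+ 1.96 x 5.66 = -31.1% to -8.9%, outside 15% either way. This holds generally. If the 95% interval lies within +/-15%, so does the narrower 90% interval, and the sequential rule then passes under either sign. Any trial whose verdict depends on the sign must therefore fail the symmetric check. That check can also fail for other reasons, so it supports the conclusion but does not prove it.

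**The case for a change.** The best case for a change is that the fragment is the SAP's only operational statement of the RD contrast. The one hint of level order, the label on the PK line, puts ABP 798 first. Carried over to the primary model, that gives rituximab minus ABP 798. Quality control compares output with a specification, so the direction belongs in the specification, as it does for the ratio measures. SAP section 1 already foresees a final version before database lock, so a few words would cost nothing.

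The facts in this argument stand: the signs differ, no level order is given, and no subtraction is written in the visible text. The inference from them does not. Carrying the PK label over assumes a shared coding that neither document states. The code is offered only as an illustration, with the dataset, response variable, covariates and label all left to be filled in. Contrast coefficients written before the coding exists cannot override the decision rule in the prose, and whoever fills in the label must decide the direction by reading that rule.

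SAP section 9 tabulates endpoints by treatment. Section 10 requires independent reprogramming of numeric table results and review by a senior statistician outside the team. The table shells are a separate document (SAP Appendix 4) and may state the direction. On the PK side a reversed line would, for example, turn a ratio of 1.10 into 1/1.10 = 0.91. The prose and the label already give the direction, and no acceptance limits for the ratio are set, so no decision would change.

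**Conclusion.** No change to the plan follows. The margin labels admit one reading, ABP 798 minus rituximab, and an analyst who follows the prose obtains a sound primary result. What remains is an unwritten convention and two code templates that do not share a sign. That is an editorial matter, settled when the treatment variable is coded and the estimate is labelled.

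The large figures (97 to 99% passing at a true 15-point deficit, 56 to 62% at 25 points) are arithmetically right but conditional. They need a reversed primary line, which the documents do not show. They also need that line to go unnoticed beside arm-level rates, a second programmer and a senior review. They rest on assumed rituximab response rates of 75 to 85% and on unadjusted Wald limits in place of the planned stratification-adjusted model. Sample size, alpha and margins are unaffected.

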9.5.1.2 SECONDARY ANALYSIS

To assess the robustness of the primary ORR analysis results, the primary analysis will be repeated using the central, independent, blinded radiologists' and oncologist's assessments on the PP analysis set according to actual treatment received and using the FAS and the investigator's assessment of disease.

The RD for ORR by week 28 will also be examined in the subgroups as defined by the baseline covariates in [Section 4.4](#). A forest plot will be created to summarize the variability in the RDs across the subgroups. In each case, the RDs and both 90% and 95% CIs will be calculated using the methods described in [Section 9.5.1.1](#).

9.5.2 Methods for Handling Dropouts and Missing Data

Subjects without measurable disease at baseline or without post-baseline disease assessments will be counted as nonresponders in calculating the ORR.

9.5.3 Multiplicity

Inferential analyses will only be performed for the primary endpoint; therefore no adjustment for multiplicity is needed.

9.5.4 Pooling of Sites

All sites will be pooled together for all analyses.

9.5.5 Secondary Variables

9.5.5.1 RISK DIFFERENCE FOR OVERALL RESPONSE RATE AT WEEK 12

The RD for ORR at week 12 will be summarized the same way as the analyses described in [Section 9.5.1](#). Subjects without a disease assessment at week 12 will be counted as nonresponders in calculating the RD for ORR at week 12.

9.6 PHARMACOKINETICS

Serum ABP 798 and rituximab concentrations will be summarized descriptively by treatment for each sampling visit using the safety analysis set.

The 90% CI for the geometric mean ratio (GMR) of test (ABP 798)-to-reference (rituximab) for serum concentrations at predose (trough) and immediately after the end of infusion at week 12 will be calculated.

The point estimates and 90% CI for the GMR for each visit will be estimated using an analysis of covariance model adjusted for the stratification factors as covariates as defined in [Section 4.4](#). Sample SAS code for PROC MIXED is displayed below:

```
PROC MIXED;  
  CLASS treatment <stratification variables>;  
  MODEL Natural Log PK concentration = treatment <stratification variables>;  
  ESTIMATE 'ABP 798 vs rituximab' Treatment 1 -1 / e ci alpha=0.1;  
RUN;
```

The geometric least squares mean for each treatment will be presented. The ratios of the geometric means for the comparison of the test treatment to the reference treatment will be obtained by exponentiating the difference of the means on the natural log scale. Ninety percent CIs will be obtained by exponentiating the CI for the difference between the means on the log scale.

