- ^k Subjects must have a bone marrow biopsy within 12 months before randomization. Previously confirmed positive bone marrow involvement does not need to be repeated for purposes of screening. An end-of-study biopsy is required if bone marrow involvement is identified at baseline **for complete response (CR) confirmation. If a confirmatory bone marrow assessment is not obtained, these subjects should be considered as only having a partial response (PR).**
- ^l Clinical laboratory tests will be performed at local laboratories. Additional and repeat laboratory safety testing may be performed at the discretion of the Investigator.
- ^m Serum chemistry and hematology for baseline (day 1) can be performed up to 3 days before baseline (day 1).
- ⁿ Serum or urine pregnancy tests for females of childbearing potential only at a local laboratory.
- ^o Pharmacokinetics samples will be collected at baseline on day 1/visit 1/week 1, predose at weeks 2, 3, 4, 12, and 20, and immediately after the end of infusion at week 12, and a single PK sample at week 28/EOS.
- ^p **Subjects who agree to optional additional PK sampling will also be required to have PK samples collected at 2 hours (± 1 hour) postdose at week 1 and week 4 and at visit 4a (week 5)**
- ^q Pharmacokinetics, pharmacodynamic, antidrug antibody and IgG and IgM samples will be sent to a central laboratory. Details will be provided in a laboratory manual.
- ^r Pharmacodynamic CD19+ cell count will be analyzed at baseline on day 1/week 1 and at weeks 2 (day 8), 3, 4 and 28.
- ^s Antidrug antibodies will be analyzed by Amgen or a designee. Sampling will be at baseline on day 1/week 1, prior to fifth dose at week 12, prior to the sixth dose at week 20 and at week 28/EOS. Subjects with positive antidrug antibody results will be assessed for neutralizing antibodies. Additional blood samples may be obtained to rule out antidrug antibodies.

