9.1 Screening

Unless otherwise stated, the following assessments/procedures will be performed within 28 days before randomization. Assessments/procedures performed as routine standard of care, prior to the subject signing informed consent, and according to the criteria outlined in [Section 10](#), can be used for screening purposes as long as the assessments/procedures were performed within 28 days before randomization (except for bone marrow biopsy **and CT scan**).

- informed consent form
- medical history, including history of NHL
- physical examination, including evaluation of body systems
- vital signs (systolic and diastolic blood pressure, pulse, respiration rate, and temperature)
- standard 12-lead electrocardiogram (ECG)
- ECOG performance status
- baseline CT of the neck (if palpable lymph node >1.0 cm), chest, abdomen, and pelvis **within 6 weeks before randomization**
- bone marrow biopsy within 12 months before randomization. Previously confirmed positive bone marrow involvement does not need to be repeated for purposes of screening
- clinical laboratory testing, including serology, serum chemistry, and hematology
- serum or urine pregnancy test for women of childbearing potential

At the screening assessment, all concomitant medications from 3 months before the planned start of study treatment will be recorded. Any AEs occurring during the screening period will be recorded as medical history; any SAEs will be recorded using the eCRF. SAEs will be reported as outlined in [Section 11.2.2](#). After screening but within 8 days before starting treatment, for eligible subjects the Investigator will contact the IXRS for randomization. **(Height and weight are required for IXRS randomization and must be collected within 8 days of visit 1).**

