4.4 PREDETERMINED COVARIATES AND PROGNOSTIC FACTORS

Unless stated otherwise, the following stratification factors will be adjusted as covariates in the model, be used as stratification variables in stratified analysis, or be used to examine efficacy in subgroups:

- Geographic region (Eastern Europe vs. Western Europe/Other vs. North America vs. Japan),
- Age (> 60 vs. ≤ 60 years)

Primary analyses that are intended to evaluate the treatment effect will be based on the IXRS stratification values, regardless of the subject's eCRF stratification values. For subgroup analyses where the subgroup factor is a stratification variable, an analysis similar to the primary analysis (except the inclusion of the subgroup factor) should be done for each subgroup defined by the eCRF values of the subgroup factor.

In addition, the following baseline covariates may be used for further exploration in subgroups or in multivariate analyses:

- Follicular lymphoma international prognostic index (FLIPI) (low, intermediate, high)
- Presence of B symptoms (yes vs. no)

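### The week-12 PK model is valid but uses no continuous baseline predictor; prespecifying body weight and baseline CD19+ count could tighten the geometric mean ratio intervals at almost no cost

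*SAP*

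**What the plan says.** SAP Section 9.6 gives one model for both week-12 endpoints. The GMR and its 90% CI "will be estimated using an analysis of covariance model adjusted for the stratification factors as covariates". The sample code reads "MODEL Natural Log PK concentration = treatment <stratification variables>" and takes the interval from "ESTIMATE 'ABP 798 vs rituximab' Treatment 1 -1 / e ci alpha=0.1". The stratification variables stand in the CLASS statement, so both enter as categories.

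SAP Section 4.4 names them: "Geographic region (Eastern Europe vs. Western Europe/Other vs. North America vs. Japan" as the four region levels, and "Age (> 60 vs. ≤ 60 years" as the two age levels. It adds that "the following baseline covariates may be used for further exploration in subgroups or in multivariate analyses", but that list holds only FLIPI and B symptoms. Weight and CD19+ count are not on it.

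Both are collected before dosing. Protocol Section 9.1 states that "Height and weight are required for IXRS randomization". A footnote to the schedule in Protocol Section 8.6.1 states that "Pharmacodynamic CD19+ cell count will be analyzed at baseline on day 1/week 1", and Section 9.2 makes that sample a pretreatment one.

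Protocol Section 12.6.5 specifies an analysis of covariance, names no covariates, and leaves further detail to the SAP.

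**The concern.** Protocol Section 6.4 lists peak and trough concentration among the measures on which the study is meant to show no clinically meaningful difference. The GMR with its 90% CI is the only between-arm PK estimate planned, so the width of that interval decides how informative the PK evidence is.

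The model is labelled an analysis of covariance but has no continuous covariate. Region and a two-level age factor were chosen to stratify randomization; neither document presents them as predictors of antibody concentration. Body size and the baseline number of target cells are plausible predictors. Treatment cannot affect either, because both are measured before the first dose. Adjusting for them would keep the treatment contrast unbiased and, if they do predict concentration, would reduce residual variance. What is at stake is precision only.

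**Working it through.** The readable text gives no PK variability, power, GMR limits or interval width, and the sample-size rationale in Protocol Section 12.2 is blacked out. There is therefore no planned figure to reproduce. The one available check is the level: alpha = 0.1, two-sided, gives a 90% interval, which agrees with the text.

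**Inputs from the documents.** 250 subjects, 125 per arm (SAP Section 3). The SAP model has 6 parameters: intercept 1, treatment 1, region 3, age 1. Adding two continuous covariates makes 8.

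**Assumptions.** The between-subject CV of concentration, and R², the share of residual log-concentration variance that weight and CD19+ explain beyond region and age. All 250 subjects are taken as evaluable.

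**Formula.** The half-width of the 90% CI on the log scale is

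h = t(0.95, df) × σ × √(1 − R²) × √(2/n) × √(1 + k/df), with σ = √ln(1 + CV²).

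Here k is the number of added covariates, and the last factor allows for chance imbalance in them.

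**SAP model, CV 50%.** σ = √ln(1.25) = 0.472; df = 250 − 6 = 244; t = 1.651; √(2/125) = 0.1265. So h = 1.651 × 0.472 × 0.1265 = 0.0987. With an observed GMR of 1.00 the interval is 0.906 to 1.104. At CV 30% it is 0.941 to 1.063, and at CV 80% it is 0.863 to 1.158.

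**With two covariates.** df = 250 − 8 = 242 and √(1 + 2/242) = 1.004. The change in t is negligible, so the width ratio is about 1.004 × √(1 − R²) and does not depend on the CV.

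| Assumed R² | Width ratio, adjusted to SAP model | 90% CI at CV 50%, GMR 1.00 |
|---|---|---|
| 0 | 1.004 | 0.906 to 1.104 |
| 0.02 | 0.994 | 0.907 to 1.103 |
| 0.05 | 0.979 | 0.908 to 1.101 |
| 0.10 | 0.953 | 0.910 to 1.099 |
| 0.20 | 0.898 | 0.915 to 1.093 |
| 0.30 | 0.840 | 0.920 to 1.086 |

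With 100 evaluable per arm the ratios hardly move (1.005 at R² 0, 0.980 at 0.05, 0.841 at 0.30).

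**Break-even.** The ratio equals 1 when 1 − R² = 1/(1 + 2/242), that is at R² = 0.008. The covariates need to explain only about 0.8% of residual variance to pay for themselves.

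**Simulation check.** 4,000 trials of 250 subjects were run per R² value, with region and age in both models. Mean width ratios were 1.004, 0.994, 0.978, 0.953, 0.898 and 0.840, in the order of the table. The adjusted interval was the narrower one in 18% of trials at R² 0, 68% at 0.02, 95% at 0.05 and over 99% at 0.10.

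**Missing baselines.** PROC MIXED drops a record whose covariate is missing. If a fraction m of subjects is lost that way, the gain disappears when 1 − m = (1 − R²) × (1 + 2/242). At R² 0.05 this gives m = 1 − 0.95 × 1.0083 = 4.2%; at R² 0.10, m = 1 − 0.90 × 1.0083 = 9.3%. A small gain is easily lost without a missing-value rule.

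**The case against.** The strongest case against acting is that nothing in the plan is wrong. Adjusting for the randomization factors is ordinary practice and matches SAP Section 4.4 and the primary response model. Randomization keeps the GMR unbiased, the interval is valid, and a slightly wide interval is conservative for a similarity claim. All of that stands.

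The benefit is also unproven. Protocol Section 8.5.1 sets each dose in mg/m² from pre-treatment height and weight, so weight already acts through the dose; what it still predicts is unknown and may differ between trough and end of infusion. For CD19+, a day-1 count would have to predict concentrations at week 12, after four weekly infusions and with depletion assessed from day 8. Neither document reports such a relationship. This stands too, and it is why the gain has to be stated conditionally. It does not show that R² is zero: dose is scaled to body surface area and not to weight, and dose scaling says nothing about the CD19+ count.

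Availability differs between the two. Weight is secure because randomization requires it. CD19+ is a scheduled central-laboratory sample, so some values may be missing, and a log transform needs a rule for zeros. Both are reasons to write the rules down.

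A reader might infer that the planned intervals are wider than they need to be. The documents do not support that, since it presupposes an R² that they do not give; at R² 0 the enlarged model is the slightly wider one. A reader might also infer that the PK comparison is flawed because an analysis of covariance lacks a continuous covariate. The label is loose, but the inference from the model is sound.

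**Conclusion.** The point holds as a conditional recommendation on precision. The SAP model adjusts for region and age group only, and two pre-dose measurements already in the schedule are left out.

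The trade-off is lopsided: a loss of about 0.4% in width if the covariates are useless, against a gain of about 2%, 5% or 16% if they explain 5%, 10% or 30% of residual variance. Ignoring the small cost of the two extra parameters, those shares correspond to 1/(1 − R²) = 1.05, 1.11 and 1.43 times the subjects. All of these sizes rest on assumed R² values, and the example intervals also on an assumed CV and full evaluability.

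No planned conclusion turns on it. SAP Section 9.5.3 confines inference to the primary endpoint, and the readable text sets no GMR acceptance limits. The priority is low.

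**What to change.** In SAP Section 9.6, add baseline body weight and log baseline CD19+ count as continuous covariates to the PROC MIXED model for both week-12 endpoints, outside the CLASS statement. State three things with them:

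- how a missing baseline is handled, for example by the mean over both arms combined, so that no subject drops out of the fit;
- how a zero or below-quantification CD19+ count is handled before the log is taken;
- that the present model, with region and age group only, is reported as supportive.

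Fix this before unblinding, since covariates chosen later would look data-driven. The cost is two model terms, two degrees of freedom and the short rules above. No new data are needed. Protocol Section 12.6.5 leaves the detail to the SAP, so its text need not change, and the SAP Introduction already foresees a final version before database lock.
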